5.2.4 Electrocardiogram

The 12-lead ECGs must be administered by a qualified technologist as scheduled in the [flowchart](#). The investigator or a designee will evaluate whether the ECG is normal or abnormal and assess clinical relevance. ECGs may be repeated for quality reasons.

Additional ECGs may be recorded for safety reasons. Dated and signed printouts of ECG with findings should be documented in patient's medical record. Clinically relevant abnormal findings will be reported either as baseline condition (if identified at the screening visit) or otherwise as AEs and will be followed up and / or treated as medically appropriate.

5.2.5 Other safety parameters

None

5.2.6 Assessment of adverse events

5.2.6.1 Definitions of AEs

5.2.6.1.1 Adverse event

An AE is defined as any untoward medical occurrence in a patient or clinical investigation subject administered a medicinal product and which does not necessarily have to have a causal relationship with this treatment.

An AE can therefore be any unfavourable and unintended sign (including an abnormal laboratory finding), symptom, or disease temporally associated with the use of a medicinal product, whether considered related or not.

The following should also be recorded as an AE in the CRF and BI SAE form (if applicable):

- Worsening of the underlying disease if certain conditions are met – refer to section [5.2.6.2.3](#)

- Worsening of pre-existing conditions other than the underlying disease
- Changes in vital signs, ECG, physical examination and laboratory test results, if they are judged clinically relevant by the investigator.

If such abnormalities already exist prior to trial inclusion, they will be considered as baseline conditions and should be collected in the eCRF only.

5.2.6.1.2 Serious adverse event

A serious adverse event (SAE) is defined as any AE, which fulfils at least one of the following criteria:

- results in death,
- is life-threatening, which refers to an event in which the patient was at risk of death at the time of the event; it does not refer to an event that hypothetically might have caused death if more severe,
- requires inpatient hospitalisation or prolongation of existing hospitalisation (except planned hospitalization for tumor resection),
- results in persistent or significant disability or incapacity,
- is a congenital anomaly / birth defect,
- is deemed serious for any other reason if it is an important medical event when based on appropriate medical judgement which may jeopardise the patient and may require medical or surgical intervention to prevent one of the other outcomes listed in the above definitions. Examples of such events are intensive treatment in an emergency room or at home for allergic bronchospasm, blood dyscrasias or convulsions that do not result in hospitalisation or development of dependency or abuse.

5.2.6.1.3 AEs considered “Always Serious”

In accordance with the European Medicines Agency initiative on Important Medical Events, Boehringer Ingelheim has set up a list of AEs, which by their nature, can always be considered to be “serious” even though they may not have met the criteria of an SAE as defined above.

The latest list of “Always Serious AEs” can be found in the eDC system. A copy of the latest list of “Always Serious AEs” will be provided upon request. These events should always be reported as SAEs as described in section [5.2.6.2](#).

Every occurrence of cancer of new histology must be classified as a serious event regardless of the time since the administration of the trial medication and must be reported as described in section [5.2.6.2](#), subsections “AE Collection” and “AE reporting to sponsor and timelines”.

5.2.6.1.4 Adverse events of special interest

The term adverse events of special interest (AESI) relates to any specific AE that has been identified at the project level as being of particular concern for prospective safety monitoring and safety assessment within this trial, e.g. the potential for AEs based on knowledge from other compounds in the same class. AESIs need to be reported to the sponsor’s

Pharmacovigilance Department within the same timeframe that applies to SAEs. Please see section [5.2.6.2.1](#).

The following are considered as AESIs:

Infusion related reactions

As with any mAb, hypersensitivity reactions to the administration of IMP are possible. Appropriate drugs and medical equipment to treat acute anaphylactic reactions must be immediately available, and trial personnel must be trained to recognize and treat anaphylaxis. The trial site must have immediate access to emergency resuscitation teams and equipment in addition to the ability to admit patients to an intensive care unit if necessary.

The following terms describe those events that are to be considered potential infusion-related AEs. Regardless of grade, these events are considered as AESIs and must be reported to the Sponsor Drug Safety Department within 24 hours of the knowledge of the event (refer to Section [5.2.6.2](#)):

- Allergic reaction
- Anaphylaxis
- Cytokine-release syndrome
- Serum sickness
- Infusion reactions
- Infusion-like reactions

If the Investigator determines that another event (not on the list) may be a potential infusion-related AE, the Investigator may also report that event as an AESI.

Management of infusion related reactions (IRR):

As a routine precaution, patients enrolled in this trial must be observed for at least 4 hours post-infusion of study drugs, with immediate access to emergency resuscitation teams and equipment in addition to the ability to admit patients to an intensive care unit if necessary.

Monitoring will include measurement of body temperature, heart rate, and blood pressure at regular intervals. Patients will be assessed for signs or symptoms of IRR, e.g. hypotension, hypoxia, tachycardia, fever, nausea, fatigue, headache, myalgias, and malaise.

Patients will be informed about possible signs and symptoms of IRR during, or after, administration of study drugs.

The following recommendations for the management of IRR regarding administration of study drugs should be considered by the Investigator as guidance:

Proprietary confidential information © 2022 Boehringer Ingelheim International GmbH or one or more of its affiliated companies

- Regarding premedication please see section 4.1.3.
- Grade \leq 2: In the event of an infusion-related reaction \leq Grade 2, the infusion rate of study drug(s) may be decreased by 50%, or interrupted, until resolution of the event and resumed at 50% of the initial rate until completion of the infusion. In case infusion must be stopped due to infusion related reactions (IRR) or similar situation, the duration of infusion can be prolonged up to 6 hours for BI 765063, or to 3 hours for ezabenlimab. Infusion duration for BI 765063 beyond 6 hours may be possible on a case-by-case bases after discussion with the sponsor. The details of dose preparation as well as the infusion duration are specified in “Instruction for Pharmacists”.
- Grade 3 or higher in severity at any time point during the infusion of study drug, the infusion has to be permanently discontinued.

Immune-related adverse event (irAE)

Immune-related AEs are AEs associated with immunotherapy treatments that appear to be associated with the immune therapy's mechanism of action. These adverse reactions, which can be severe, may involve the gastrointestinal, skin, liver, endocrine, respiratory, renal, or other organ systems. The sponsor has defined a list of potential irAEs which need to be reported as irAEs in Section 10.3. If an investigator determines another event (not on the list) should be a potential irAE, the investigator may also report that event as an AESI.

Hepatic injury

A hepatic injury is defined by the following alterations of hepatic laboratory parameters:

- For patients with abnormal liver function at baseline (AST and/or ALT $>$ ULN)
 - an elevation of AST and/or ALT \geq 5 fold ULN combined with an elevation of total bilirubin \geq 2 fold ULN measured in the same blood draw sample, with the exclusion of the causes due to underlying diseases, and/or
 - Marked peak aminotransferase (ALT, and/or AST) elevations \geq 10 fold ULN
- For patients with normal liver function at baseline (ALT, AST, and bilirubin within normal limits at baseline):
 - an elevation of AST and/or ALT \geq 3 fold ULN combined with an elevation of total bilirubin \geq 2 fold ULN measured in the same blood draw sample, and/or
 - Marked peak aminotransferase (ALT, and/or AST) elevations \geq 10 fold ULN

These lab findings constitute a hepatic injury alert and the patients showing these lab abnormalities need to be followed up according to the “DILI checklist” provided in the ISF and EDC.

[figure not shown]

Figure 5.2.6.1.4:1 Potential severe DILI reporting –in case of a DILI please follow the above procedure on how to report the DILI as an AESI.

In case of clinical symptoms of hepatic injury (icterus, unexplained encephalopathy, unexplained coagulopathy, right upper quadrant abdominal pain, etc.) without lab results (ALT, AST, total bilirubin) available, the investigator should make sure these parameters are analysed, if necessary in an unscheduled blood test. Should the results meet the criteria of hepatic injury alert, the procedures described in the DILI checklist should be followed

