5.2.6.2.3 Exemptions to SAE reporting

The outcome "disease progression" is used to assess trial endpoints for the analysis of efficacy and as such is exempted from AE/SAE reporting. Signs and symptoms of disease progression which can exclusively be determined to be due to the progression of the underlying malignancy and meet the expected pattern of disease progression for the disease under study are also exempted from AE/SAE reporting.

Disease progression of the patient's underlying malignancy will be recorded on the appropriate pages of the eCRF as part of efficacy data collection only. It will not be recorded on the AE page in the eCRF and will not be reported on the SAE Form even when it meets standard seriousness criteria.

Lab values meeting the potential severe DILI definition in section must always be reported as AESI, even if the most likely cause is disease progression. No exemption to AE reporting applies.

When there is evidence suggesting a causal relationship between the trial drug(s) and the progression of the underlying malignancy, the event must be recorded as an SAE on the AE page in the eCRF and reported as an SAE on the SAE Form.

Exempted events are monitored at appropriate intervals

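### In one of the four hepatic-injury criteria, attribution to underlying disease can switch off an AESI report that Protocol 5.2.6.2.3 says is always due

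*Protocol*

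**What the plan says.** Protocol 5.2.6.1.4 lists hepatic injury among the AESIs and defines it by laboratory values, separately for abnormal and normal baseline liver tests. The first group is headed "For patients with abnormal liver function at baseline", meaning AST and/or ALT above ULN. Its combined criterion (AST/ALT at least 5 × ULN with total bilirubin at least 2 × ULN) ends with a causal condition: "with the exclusion of the causes due to underlying diseases". The group's second criterion, introduced as "Marked peak aminotransferase (ALT, and/or AST) elevations" and set at 10 × ULN or more, has no such condition. Neither does either criterion for patients with normal baseline tests.

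The section continues: "These lab findings constitute a hepatic injury alert". The patient is then followed up under the DILI checklist, and the figure caption treats a DILI case as an AESI to be reported. AESIs go to the sponsor within 24 hours (Protocol 5.2.6.2.1).

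Protocol 5.2.6.2.3 exempts progression of the underlying malignancy from AE/SAE reporting and then makes an exception for the liver: "Lab values meeting the potential severe DILI definition in section must always be reported as AESI, even if the most likely cause is disease progression". The next sentence says that no exemption applies.

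**The concern.** A laboratory alert is useful because it fires before anyone decides on a cause. In this one criterion the investigator must decide on the cause first. If the answer is the underlying disease, the value falls outside the definition, so the rule in 5.2.6.2.3 has nothing to act on. Yet that rule was written for the case in which the cancer looks like the explanation.

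Patients who could meet the criterion may enter the trial. Table 3.3.2:1 admits AST and ALT up to 2.5 × ULN. Its footnote waives the hepatic limits for biologic or drug-related causes and for bilirubin raised by tumor obstruction. The protocol counts immune-related events and DILI among the potentially severe risks (Table 1.4.2:1) and relies on timely detection and follow-up of liver values to mitigate the latter. A missed alert would weaken that mitigation in patients whose raised baseline already makes attribution difficult.

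**Working it through.** No arithmetic applies. The check compares the definition in 5.2.6.1.4 with the reporting rule in 5.2.6.2.3, criterion by criterion.

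| Baseline AST/ALT | Criterion | Exclusion by cause in 5.2.6.1.4? | Conflict with 5.2.6.2.3? |
|---|---|---|---|
| Above ULN | AST/ALT ≥ 5 × ULN and bilirubin ≥ 2 × ULN | Yes | Yes |
| Above ULN | AST/ALT ≥ 10 × ULN | No | No |
| Normal | AST/ALT ≥ 3 × ULN and bilirubin ≥ 2 × ULN | No | No |
| Normal | AST/ALT ≥ 10 × ULN | No | No |

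**Range of values.** The two abnormal-baseline criteria are joined by and/or. A rise to 10 × ULN or more is therefore captured by the second criterion whatever its cause. The gap is left with AST/ALT from 5 to below 10 × ULN, bilirubin at least 2 × ULN in the same sample, and attribution to underlying disease. All of these conditions must hold together.

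**Which cause.** 5.2.6.2.3 names disease progression only. 5.2.6.1.4 speaks of underlying diseases in the plural, which may be wider. The malignancy is covered by both: 5.2.6.2.3 calls it the underlying malignancy, and 5.2.6.1.1 refers to that section for worsening of the underlying disease. The direct contradiction is therefore confined to liver changes attributed to the cancer.

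**Other reporting routes for such a case.**
- Table 10.3:1 makes hepatic events AESIs from Grade 2, but only when judged immune-related. A case attributed to the cancer fails that condition.
- The SAE route is closed for progression by 5.2.6.2.3 itself, even when seriousness criteria are met.

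**What does not depend on the clause.**
- All AEs are collected on the CRF from consent to the patient's end of trial (5.2.6.2), whether or not they are AESIs. Clinically relevant laboratory changes are AEs (5.2.3, 5.2.6.1.1) and are graded by CTCAE (5.2.6.1.5). One qualification applies: a finding attributed exclusively to progression can fall under the general exemption in 5.2.6.2.3, which is the exemption the DILI sentence is there to override.
- The primary endpoint and stopping rule (2.1.2, 7.2.3) count treatment-related grade 3 or higher AEs and treatment-related surgical delay. They count neither AESIs nor hepatic-injury alerts. Relatedness is a separate judgement (5.2.6.1.6).

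**The case against.** The best defence is literal. A value excluded by cause never meets the definition, so 5.2.6.2.3 is not breached. An attribution clause for patients who start with abnormal liver tests may also be deliberate. The first argument does not resolve the conflict: it leaves the words about disease progression with no effect for this criterion. The second may be right, but the protocol does not say so, and 5.2.6.2.3 makes no allowance for it.

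Two further objections stand in part. The DILI reporting figure and the checklist are not available here and may say how attribution is handled. Liver changes from the cancer should also be uncommon, because metastatic disease without curative surgical intent is excluded (3.3.3, criterion 10).

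A reader might also infer three stronger things that the documents do not support.
- **Every patient with abnormal baseline tests is affected.** Only those who meet all the conditions set out in the working are.
- **The contradiction extends to hepatitis B or C, HIV or drug-raised transaminases.** 5.2.6.2.3 names only disease progression. A viral flare stays reportable as an AE, and as an SAE if serious. A drug effect is not an underlying disease.
- **A missed alert could tip a stopping decision, for example at the boundary of 5 in 15 patients.** The count does not use alerts, and a case attributed to underlying disease would ordinarily be judged unrelated even if the clause were removed. A DILI work-up might revise a mistaken attribution, but nothing in the documents allows a figure to be put on that.

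**Conclusion.** The inconsistency is real and narrow: one criterion in four, a limited range of transaminase values, and a direct clash only where the underlying disease is the malignancy. At stake are early notification and structured follow-up of possible liver injury. No estimate, boundary or operating characteristic changes.

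The documents give no frequency for such cases. The SAP (sections 3 and 6.4) reports early discontinuation with two treated patients and plans only a patient profile listing, so the practical effect on this trial is small. The wording matters mainly if it is carried into other protocols.

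The conclusion rests on two assumptions. The first is that the potential severe DILI definition cited in 5.2.6.2.3 is the one in 5.2.6.1.4; the section number is missing from the text, but the figure caption in 5.2.6.1.4 uses the same term and no other definition appears. The second is that the unseen figure and checklist do not already settle the matter.

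**What to change.** Reconcile 5.2.6.1.4 and 5.2.6.2.3 so that one AESI reporting trigger applies. One way is to make the trigger for the combined criterion in abnormal-baseline patients depend on the laboratory values alone, consistent with the no-exemption sentence in 5.2.6.2.3, and to record the suspected cause afterwards on the DILI checklist. If the sponsor wants to keep an attribution clause, 5.2.6.2.3 should state the exception and the reason for it. In either case the missing section reference in 5.2.6.2.3 should be confirmed. This concerns reporting only and takes no position on how such patients should be managed.

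The cost is one amended clause and, if attribution is removed from the trigger, a few additional 24-hour reports that may later be put down to underlying disease.

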5.2.6.1.5 Intensity (severity) of AEs

The intensity (severity) of adverse events should be classified and recorded in the CRF according to the Common Terminology Criteria for Adverse Events (CTCAE), Version 5.0.

5.2.6.1.6 Causal relationship of AEs

Medical judgement should be used to determine the relationship between the adverse event and the BI investigational compound, considering all relevant factors, including pattern of reaction, temporal relationship, de-challenge or re-challenge, confounding factors such as concomitant medication, concomitant diseases and relevant history.

Arguments that may suggest that there is a reasonable possibility of a causal relationship could be:

- The event is consistent with the known pharmacology of the trial drug.
- The event is known to be caused by or attributed to the drug class.

- A plausible time to onset of the event relative to the time of drug exposure.
- Evidence that the event is reproducible when the drug is re-introduced.
- No medically sound alternative aetiologies that could explain the event (e.g. pre-existing or concomitant diseases, or co-medications).
- The event is typically drug-related and infrequent in the general population not exposed to drugs (e.g. Stevens-Johnson syndrome).

Arguments that may suggest that there is no reasonable possibility of a causal relationship could be:

- No plausible time to onset of the event relative to the time of drug exposure is evident (e.g. pre-treatment cases, diagnosis of cancer or chronic disease within days / weeks of drug administration; an allergic reaction weeks after discontinuation of the trial drug concerned).
- Continuation of the event despite the withdrawal of the medication, considering the pharmacological properties of the compound (e.g. after 5 half-lives).
Of note, this criterion may not be applicable to events whose time course is prolonged despite removing the original trigger.
- There is an alternative explanation, e.g. situations where other drugs or underlying diseases appear to provide a more likely explanation for the observed event than the drug concerned.
- Disappearance of the event even though the trial drug treatment continues or remains unchanged.

5.2.6.2 Adverse event collection and reporting

AE Collection

The investigator shall maintain and keep detailed records of all AEs in the patient files. The following must be collected and documented on the appropriate CRF(s) by the investigator:

- From signing the informed consent onwards until the individual patient's end of trial (including the Follow up Period):
all AEs (serious and non-serious) and all AESIs.
- After the individual patient's end of trial:
the investigator does not need to actively monitor the patient for new AEs but should only report any occurrence of cancer and trial drug related SAEs and trial drug related AESIs of which the investigator may become aware of by any means of communication, e.g. phone call. Those AEs should be reported on the BI SAE form (see section [5.2.6.2.1](#)), but not on the CRF.

The rules for Adverse Event Reporting exemptions still apply, please see section [5.2.6.2.3](#).

5.2.6.2.1 AE reporting to the sponsor and timelines

The investigator must report SAEs, AESIs, and non-serious AEs which are relevant for the reported SAE or AESI, on the BI SAE form to the sponsor's unique entry point within 24 hours of becoming aware of the event, the country specific process will be specified in the ISF. The same timeline applies if follow-up information becomes available. In specific occasions, the investigator could inform the sponsor upfront via telephone. This does not replace the requirement to complete the BI SAE form.

With receipt of any further information to these events, a follow-up SAE form has to be provided. For follow-up information the same rules and timeline apply as for initial information. All (S)AEs, including those persisting after individual patient's end of trial must be followed up until they have resolved, have been assessed as "chronic" or "stable", or no further information can be obtained.

5.2.6.2.2 Pregnancy

In rare cases, pregnancy might occur in a clinical trial. Once a patient has been enrolled in the clinical trial and has taken trial medication, the investigator must report any drug exposure during pregnancy in a trial participant immediately (within 24 hours) by means of Part A of the Pregnancy Monitoring Form to the sponsor's unique entry point.

The outcome of the pregnancy associated with the drug exposure during pregnancy must be followed up and reported to the sponsor's unique entry point on the Pregnancy Monitoring Form for Clinical Studies (Part B).

The ISF will contain the Pregnancy Monitoring Form for Clinical Studies (Part A and B).

As pregnancy itself is not to be reported as an AE, in the absence of an accompanying SAE and / or AESI, only the Pregnancy Monitoring Form for Clinical Studies and not the SAE form is to be completed. If there is an SAE and / or AESI associated with the pregnancy an SAE form must be completed in addition.

5.2.6.2.3 Exemptions to SAE reporting

The outcome "disease progression" is used to assess trial endpoints for the analysis of efficacy and as such is exempted from AE/SAE reporting. Signs and symptoms of disease progression which can exclusively be determined to be due to the progression of the underlying malignancy and meet the expected pattern of disease progression for the disease under study are also exempted from AE/SAE reporting.

Disease progression of the patient's underlying malignancy will be recorded on the appropriate pages of the eCRF as part of efficacy data collection only. It will not be recorded on the AE page in the eCRF and will not be reported on the SAE Form even when it meets standard seriousness criteria.

Lab values meeting the potential severe DILI definition in section must always be reported as AESI, even if the most likely cause is disease progression. No exemption to AE reporting applies.

When there is evidence suggesting a causal relationship between the trial drug(s) and the progression of the underlying malignancy, the event must be recorded as an SAE on the AE page in the eCRF and reported as an SAE on the SAE Form.

Exempted events are monitored at appropriate intervals

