3.3.3 Exclusion criteria

Patients must not enter the trial if any of the following exclusion criteria are fulfilled:

1. Patients who are deemed to be at high risk for colonic obstruction and/or perforation per investigator assessment.
2. Patients eligible for neoadjuvant therapy (chemotherapy, radiotherapy, chemoradiotherapy) as standard of care.
3. Major surgery (major according to the investigator's assessment) performed within 4 weeks prior to administration of trial medication.
4. Patients who must or wish to continue the intake of restricted medications (see section [4.3.2.1](#)) or any drug considered likely to interfere with the safe conduct of the trial.
5. Patients not expected to comply with the protocol requirements or not expected to complete the trial as scheduled (e.g. chronic alcohol or drug abuse or any other

condition that, in the investigator's opinion, makes the patient an unreliable trial participant).

6. Previous enrolment in this trial.
7. Currently enrolled in another investigational device or drug trial, or less than 30 days since ending another investigational device or drug trial(s) or receiving other investigational treatment(s).
8. Patients who have had [REDACTED] prior to entering the study for a different primary tumor, or those that have received locoregional therapy (radiation, chemoembolization, etc.) for the target lesion that will be biopsied and subsequently resected. Previous therapy for a different cancer (a different primary) is acceptable.
9. Prior immune checkpoint inhibitor therapy.
10. Patients with metastatic or recurrent disease, for which the intent of surgery would not be curative.
11. Uncontrolled intercurrent illness including, but not limited to, ongoing or active infection requiring antibiotics (except antibiotics to be completed 4 weeks before initiation of treatment), symptomatic congestive heart failure, unstable angina pectoris, or psychiatric illness/social situations that would limit compliance with study requirements.
12. Patients who are pregnant or nursing or who plan to become pregnant while in the trial.
13. Has a diagnosis of primary immunodeficiency or is receiving systemic steroid therapy or any other form of immunosuppressive therapy within 7 days prior to the administration of trial treatment. Patients on chronic steroids (more than 4 weeks at stable dose) equivalent to \leq 10mg prednisone will not be excluded.

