10.3 IMMUNE-RELATED ADVERSE EVENTS OF SPECIAL INTEREST

This table defines immune-related AEs that must be reported as AESIs if they occur after exposure to the trial treatment. For each category examples are provided, but these are not exhaustive.

Table 10.3: 1 Immune-related adverse events of special interest

Immune-related adverse events of special interest
Pneumonitis (report as AESI if an irAE is \geq Grade 2) 
• Acute interstitial pneumonitis• Interstitial lung disease• Pneumonitis
Colitis (report as AESI if an irAE is \geq Grade 2 or any grade resulting in dose modification or use of systemic steroids to treat the AE) 
• Intestinal obstruction• Colitis• Colitis microscopic• Enterocolitis• Enterocolitis haemorrhagic• Gastrointestinal perforation• Necrotising colitis• Diarrhea
Endocrine (report as AESI if an irAE is \geq Grade 3 or \geq Grade 2 and resulting in dose modification or use of systemic steroids to treat the AE)

Immune-related adverse events of special interest

- Adrenal insufficiency
- Hyperthyroidism
- Hypophysitis
- Hypopituitarism
- Hypothyroidism
- Thyroid disorder
- Thyroiditis
- Hyperglycaemia, if \geq Grade 3 and associated with ketosis or metabolic acidosis

Endocrine (report as AESI for any grade)

- Type 1 diabetes mellitus (if new onset)

Haematologic (report as AESI if an irAE is \geq Grade 3 or any grade resulting in dose modification or use of systemic steroids to treat the AE)

- Autoimmune haemolytic anaemia
- Aplastic anaemia
- Thrombotic thrombocytopenic purpura
- Idiopathic (or immune) thrombocytopenia purpura
- Disseminated intravascular coagulation
- Haemolytic-uraemic syndrome
- Any Grade 4 anaemia regardless of underlying mechanism

Hepatic (report as AESI if an irAE is \geq Grade 2, or any grade resulting in dose modification or use of systemic steroids to treat the AE)

- Hepatitis
- Autoimmune hepatitis
- Transaminase elevations (ALT and/or AST)

Infusion Reactions (report as AESI for any grade)

- Allergic reaction
- Anaphylaxis
- Cytokine release syndrome
- Serum sickness
- Infusion reactions
- Infusion-like reactions

Neurologic (report as AESI for any grade)

- Autoimmune neuropathy
- Guillain-Barre syndrome
- Demyelinating polyneuropathy
- Myasthenic syndrome

Immune-related adverse events of special interest

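### The progression exemption rests on an efficacy rationale that matches no progression-defined endpoint, and it can keep a tumour-attributed obstruction or perforation off the AE and SAE record

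*Protocol*

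**What the plan says.** Protocol 5.2.6.2.3 gives the reason for the exemption: progression "is used to assess trial endpoints for the analysis of efficacy and as such is exempted from AE/SAE reporting". A second sentence extends it to "Signs and symptoms of disease progression which can exclusively be determined to be due to the progression of the underlying malignancy", provided that they also "meet the expected pattern of disease progression for the disease under study". Progression itself "will be recorded on the appropriate pages of the eCRF as part of efficacy data collection only", and it "will not be reported on the SAE Form even when it meets standard seriousness criteria".

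The same section sets three limits:

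- Progression with evidence of a causal link to trial drug must be recorded and reported as an SAE.
- Laboratory values meeting the severe liver-injury definition "must always be reported as AESI, even if the most likely cause is disease progression".
- Exempted events are to be monitored, but no interval, method or responsible body is named.

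Three other places bear on the point. Protocol 5.2.6.1.1 makes worsening of the underlying disease an AE only under the conditions of 5.2.6.2.3. Table 10.3:1 lists "Intestinal obstruction" and gastrointestinal perforation in its colitis row, which applies only to immune-related events. Exclusion criterion 1 in 3.3.3 bars "Patients who are deemed to be at high risk for colonic obstruction and/or perforation per investigator assessment"; section 11 records that it was added following FDA comments.

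**The concern.** Such an exemption makes sense where progression is an endpoint: the event is captured and analysed as efficacy, so reporting it again as an SAE adds noise. That argument needs an endpoint that does the capturing. Here the primary tumour stays in place between dosing and a curative resection scheduled 2 to 6 weeks later. An obstruction or perforation in that interval bears directly on safety and feasibility, which are the primary objective.

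What is at stake is reviewability. An ordinary AE judged unrelated is still on the AE page, where the sponsor can question its causality. An exempted event is not. The site's attribution then settles both the cause and whether there is an AE record to review.

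**Working it through.** The point rests on a comparison of texts. The arithmetic at the end is a side check only.

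**1. Does any endpoint use progression?** Inputs: Protocol 2.1.3, 7.2.4, the flow chart and 6.2.3.

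- Pathologic response is graded on the surgical specimen and measures regression.
- Time from treatment to surgery is a duration in days.
- Radiographic response is read by RECIST 1.1 on one pre-surgical scan. It can register progressive disease at that scan and at no other time.

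Section 7.2.4 plans a descriptive summary of radiographic response and no progression analysis. Imaging is scheduled at screening and Visit 3; the end-of-study procedures include none. So the rationale has partial support at one time point and none afterwards. The exemption itself has no end date, and 5.2.6.2 collects AEs to each patient's end of trial.

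**2. Where does a bowel obstruction or perforation go?** Inputs: Protocol 5.2.6.1.1, 5.2.6.2.3 and Table 10.3:1.

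| How the event is judged | Route under the protocol |
|---|---|
| No progression involved | AE; SAE if serious |
| Progression present, but cause mixed or uncertain | Not exclusively due to progression, so AE; SAE if serious |
| Progression with evidence of a link to trial drug | SAE |
| Immune-related and meeting the colitis-row threshold | AE and AESI |
| Exclusively due to progression and within the expected pattern | No AE, SAE or AESI route |

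The last row is the gap. Section 5.2.6.2.3 sends progression to the efficacy pages but does not say where an exempt sign or symptom is recorded. It does not define the expected pattern for resectable colorectal cancer either. For liver-injury laboratory values the section closes the same gap with an explicit override; obstruction and perforation have none.

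**3. Does this reach the primary endpoint?** Inputs: the synopsis, 2.1.2 and 7.2.3. The endpoint counts treatment-related events of grade 3 or above and treatment-related events that delay surgery. A correctly attributed tumour event does not count, with or without the exemption. Only a misattributed event would be lost.

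**4. Side check on the stopping rule.** Boundaries (7.2.3): 3 of 5, 5 of 15, 8 of 25. With event probability p, and independent binomial counts A in the first 5 patients, B in the next 10 and C in the last 10:

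P(declare) = P(A ≥ 3) + P(A ≤ 2, A+B ≥ 5) + P(A ≤ 2, A+B ≤ 4, A+B+C ≥ 8)

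| True rate | 0.1 | 0.2 | 0.3 | 0.4 | 0.5 |
|---|---|---|---|---|---|
| Table 7.5:1 | 0.02 | 0.21 | 0.60 | 0.89 | 0.98 |
| Exact | 0.020 | 0.215 | 0.605 | 0.893 | 0.986 |

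The plan's figures reproduce to within 0.01. Now assume that a share m of true composite events is misattributed and so not counted, which replaces p by p(1 − m). At a true rate of 0.40:

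- m = 5%: 0.40 × 0.95 = 0.38, P(declare) = 0.85
- m = 10%: 0.40 × 0.90 = 0.36, P(declare) = 0.80
- m = 20%: 0.40 × 0.80 = 0.32, P(declare) = 0.68

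These values of m are assumptions. The documents give no misattribution rate, so this range shows direction and is not an estimate.

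**The case against.** The case against is substantial, and much of it stands.

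- **The rationale is not baseless.** A reader might infer that the trial has no use for progression at all. The RECIST reading can record it, so the supportable statement is that no endpoint is defined by progression.
- **The exemption is narrow.** A reader might infer that every progression symptom escapes reporting. Both conditions must hold, and drug-related progression is an SAE. If inflammatory swelling and tumour growth cannot be told apart, exclusivity cannot be determined and the event remains reportable. This stands as a limit on the gap. It does not close it: the conditions are applied by the investigator, and an event judged to meet them leaves no AE entry against which that judgement can be checked.
- **Obstruction and perforation may fall outside the expected pattern,** since high-risk patients are excluded at entry. That is arguable, but the protocol leaves the pattern undefined, so the site has to decide.
- **The events are not necessarily hidden from the DRC.** Sections 3.1.1 and 7.2.8 give it efficacy results and overall data, it may meet at any time, and the sponsor's safety physician is a decision maker. This stands for progression on the efficacy pages. It does not secure presentation as a safety event with a causality judgement.
- **The stopping rule counts only related events.** A reader might put one or two exempted events at 20% to 40% of the first look (1/5 and 2/5). Those events are hypothetical, and if truly due to the tumour they would not enter the count.

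**Conclusion.** The concern holds in a limited form. The stated rationale fits no endpoint beyond one pre-surgical reading. A serious obstruction or perforation attributed exclusively to the tumour, and taken to fit an undefined pattern, has no route to the AE page, the SAE form or the AESI list, although the protocol treats these events as a concern in 3.3.3 and Table 10.3:1. The consequence is an incomplete safety record and an attribution that cannot be reviewed as a safety event.

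The documents do not support the stronger conclusion that the interim monitoring or the primary endpoint is biased by a known amount. That would need a misattribution rate, which is not given.

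The remaining effect is small. SAP sections 3, 4 and 6.4 limit the output to profile listings for two treated patients. SAP 7.8.1 promises all their adverse event data, and an exempted event would be missing from those data. Nothing in the documents indicates that one occurred.

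**What to change.** Reconcile Protocol 5.2.6.2.3 with 2.1.3, 5.2.6.1.1 and Table 10.3:1:

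1. Remove the efficacy-endpoint rationale, or restrict it to the pre-surgical RECIST reading that it can refer to.
2. Extend the no-exemption line now used for liver-injury laboratory values to intestinal obstruction and gastrointestinal perforation, from dosing to the end of the 90-day follow-up, whatever the attributed cause.
3. Record these events as AE or SAE with a separate causality judgement, and show them to the DRC.
4. If the symptom exemption is kept for other events, define the expected pattern for resectable colorectal cancer and say where exempt events are recorded and who monitors them.

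The change concerns reporting only and leaves patient management as it is. It costs a wording amendment and a few additional AE or SAE reports in a trial planned for about 50 patients. For the trial as it ended, the sponsor can check the two patients' efficacy pages and source records for any exempted event, and carry the corrected wording into any protocol that reuses this text.
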